## 8.2. Other Secondary Efficacy Analyses

The other secondary efficacy analyses will be interpreted as exploratory analyses. All secondary endpoints will be analyzed according to the prespecified assessment timepoints listed in the protocol. Statistical models will include covariates for baseline SSS, baseline neurotoxicity (Yes, No; based on the SSS neurological system subscore), age group (5-17, 18+), and, when available, the baseline value of the particular endpoint unless otherwise specified below. A sensitivity analysis will include as a covariate yes/no completion of an initial dose of antivenom prior to randomization. The methods described here are what is currently planned. However, for each analysis, we will examine the distribution of the strata pooled over treatment and placebo. If the data are unlikely to support the planned analysis or if the model fails to converge, removal of covariates and different estimation routines will be attempted and described in the CSR.

### 8.2.1. Complete SSS from Baseline through Day 7

The complete SSS (all sub-sections including pulmonary, cardiovascular, hematologic, renal, nervous system, gastrointestinal, and local wound) from baseline through Day 7 after first dose will be summarized using descriptive statistics of observed values and changes from baseline.

The post baseline complete SSS scores at each time point will be analyzed, without replacement of missing values, using a restricted maximum likelihood (REML) based repeated measures approach (MMRM). Analyses will include a random intercept and the fixed effects of treatment, baseline total SSS, age group (5-17 years,  $\geq$  18 years), baseline neurotoxicity, and visit (categorical) as covariates. The model will include a treatment-by-time interaction. An unstructured covariance model will be used to model the within-subject errors. The Kenward-Roger approximation will be used to estimate denominator degrees of freedom. If this analysis fails to converge, simpler structures (e.g., first-order compound symmetry and then autoregressive order-1 structures) will be tested in a model without treatment effect; the covariance structure and the degree of freedom approximation converging to the best fit, as determined by Akaike's Information Criterion, will be used in the full model. A description of all tested models and results from these models will be provided as an appendix in the CSR. Within this model, the estimate of interest is the effect of treatment at each time point, performed at significance level of 5%. The corresponding 95% two-sided confidence intervals will be presented at each time point of assessment.

### 8.2.2. SSS Neurologic System Subscore from Baseline through Day 3

The SSS neurologic system subscore from baseline through Day 3 after first dose will be summarized using descriptive statistics of observed values and changes from baseline. The SSS neurologic system subscore will be analyzed with a similar MMRM as the one described in [Section 8.2.1](#). The MMRM will be used to assess the treatment effect on change in SSS neurologic system subscore through Day 3. The MMRM will include treatment as fixed effect as the variable of interest, with visit and visit by treatment interaction as covariates. The model will be used to estimate the effect of treatment on SSS neurologic subscore at each assessment time

point through Day 3. Treatment effect will be summarized via LS means, p-values, and 95% two-sided confidence intervals.

This analysis will be conducted in two groups of patients: (1) subjects with a baseline SSS neurologic system subscore  $\geq 1$ ; and (2) subjects with a baseline SSS neurologic system subscore  $\geq 2$ .

Note: The effect of varespladib on neurotoxicity is supported by the observation that varespladib prevents, reverses, or delays lethality from venom neurotoxicity in animals experimentally envenomed with Mojave rattlesnake, coral snake, krait, and taipan venoms even when administered at a point when weakness is refractory to antivenom reversal (e.g., Prasarnpun 2005; Anil et al. 2010; Lewin et al. 2018a, 2018b; and Gutierrez et al. 2021). Neurologic outcomes were not selected as the focus of the primary or key secondary efficacy endpoints because of the unexpectedly small number of severely neurotoxic patients enrolled in the trial.

### 8.2.3. Coagulation Abnormalities from Baseline through Day 7

Each of the four coagulation lab values (PT, PTT, platelets, and fibrinogen) will be analyzed using a proportional odds logistic regression with five ordered categories. Categories for the lab values in each of these analyses will use those defined by the Snakebite Severity Score (Dart et al. 1996), with normal lab values receiving a score of 0 and abnormal lab values receiving a score of 1 to 4 based on the following published cutoffs.

Coagulation Parameter	0	1	2	3	4	Units
Prothrombin Time	Lab validated reference range	Above lab ref range to 20 sec	>20 to 50 sec	>50 to 100 sec	Unmeasureable or above 100 sec	Sec
Partial Thromboplastin Time	Lab validated reference range	Above lab ref range to 50 sec	>50 to 75 sec	>75 to 100 sec	Unmeasureable or above 100 sec	Sec
Platelet count	Lab validated reference range	100,000 to ref	50,000 to <100,000K	20,000 to <50,000	Less than 20,000	/mL
Fibrinogen	Lab validated reference range	100 to ref	50 to <100	Less than 50	Undetectable	mg/dL

Analysis for each of the four coagulation parameters will be run separately for each time point from Day 1 3 hours to Day 7. The models will use the following covariates: baseline SSS score, age group (5 to 17 years,  $\geq$  18 years), baseline neurotoxicity, receipt of antivenom prior to baseline (Yes, No), and country. The treatment effect will be summarized with an estimated odds ratio and tested at a 5% two-sided significance level; the corresponding 95% two-sided confidence intervals will be presented. These analysis will only include subjects with lab value-specific coagulation abnormalities (hematology subscore  $\geq$  1 as derived from the relevant coagulation lab value) at baseline.

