### 6.1.7.2. SSS-AUC7d

The AUC calculation includes the pulmonary, cardiovascular, local wound, hematologic, renal, and nervous system sections of the SSS assessment up to 7±1 days. The calculation will include the baseline assessment. All assessments within baseline and baseline + 8 days will be included in the calculation. This endpoint will be analyzed according to the missing data procedures described in [Section 6.1.4](#) above.

In order to standardize the duration of time for each SSS-AUC7d calculation, the “Day 7” SSS will be set at exactly 168 hours regardless of when it was actually assessed for this endpoint, with two exceptions:

- 1) For patients whose “Day 7” score was assessed prior to Day 7 (prior to 144 hours) and whose score is higher at the “Day 14” assessment than at the “Day 7” assessment, we will linearly interpolate between the “Day 7” and “Day 14” scores to impute the score at 168 hours.
- 2) For patients whose “Day 7” occurs on Day 10 or later (240 hours), we will linearly interpolate between “Day 3” and “Day 7” to impute the score at 168 hours.

The AUC will be calculated using the trapezoidal rule: average the SSS scores between two adjacent timepoints, multiply by the difference in time points in hours, repeating this across all time points and summing the results to obtain the total AUC across a fixed range of time. Thus the AUC at a particular timepoint  $j$  is calculated as follows.

$$AUC_j = \frac{1}{2}(SSS_j + SSS_{j-1})(t_j - t_{j-1})$$

where  $t$  is measured in hours;  $j = 1, \dots, J$ ; and  $J$  is the total number of timepoints at which SSS is measured.  $J = 6$  if all planned SSS assessments are performed. Thus the total AUC for subject  $i$  from baseline to Day 7 is as follows.

$$AUC_{i, \text{BL to Day 7}} = \frac{1}{2} \sum_{j=1}^J (SSS_{i,j} + SSS_{i,j-1})(t_{i,j} - t_{i,j-1})$$

Thus AUC is calculated for each subject with baseline and post-baseline SSS scores, subject to the constraints on missingness described above. An example of this applied in SAS is provided at [lexjansen.com/wuss/2004/posters/c\\_post\\_the\\_sas\\_calcuations\\_pdf](http://lexjansen.com/wuss/2004/posters/c_post_the_sas_calcuations_pdf)

- where: The SSS assessments  $SSS_0, SSS_1, \dots, SSS_J$  are made at times  $t_0, \dots, t_J$
- $t_0$  is the time of the initiation of the IV infusion
- $SSS_0$  is the SSS assessment at baseline

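### The MMRM in SAP 8.2.1 pairs a random intercept with an unstructured residual covariance, leaving one covariance parameter redundant and the fallback to simpler structures open to a spurious trigger

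*SAP*

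**What the plan says.** SAP 8.2.1 specifies a REML-based MMRM for the post-baseline complete SSS through Day 7. On random effects: "Analyses will include a random intercept and the fixed effects of treatment". On the residuals: "An unstructured covariance model will be used to model the within-subject errors". On inference: "The Kenward-Roger approximation will be used to estimate denominator degrees of freedom".

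The fallback reads: "If this analysis fails to converge, simpler structures (e.g., first-order compound symmetry and then autoregressive order-1 structures) will be tested". This testing is done in a model without the treatment effect, and the best-fitting structure, "as determined by Akaike's Information Criterion, will be used in the full model". The result of interest is the treatment effect at each time point, with a 5% test and a 95% confidence interval.

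Nothing in 8.2.1 says that the random intercept is dropped when the residual covariance is unstructured, or that the unstructured model is retried without it before the fallback starts. The general MMRM description in SAP 6.1.2 lists covariates and interactions and mentions no random intercept.

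Sections 8.2.4, 8.2.5 and 8.2.6 use the approach described in 8.2.1, and 8.2.2, 8.2.14 and 8.2.15 use one similar to it.

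**The concern.** A random intercept adds the same constant to every element of a subject's covariance matrix. An unstructured matrix can absorb any such constant, so the likelihood is flat in that direction. A flat direction can stop the optimiser from converging, or leave a Hessian that is not positive definite, even where the data support an unstructured matrix.

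This matters because non-convergence is what sends the analysis to simpler structures. Compound symmetry and AR(1) both assume one variance at all visits. AR(1) also gives every adjacent pair of visits the same correlation, although the gaps run from a few hours (3–4 h, 5–6 h, 8–10 h) to four days (Day 3 to Day 7). Since the target is the effect at each visit, a wrong pooled variance goes straight into the visit-specific standard errors.

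**Working it through.** The documents state no figure for this point, so the check is of identifiability.

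**Inputs**
- Visits: SAP 6.1.7.2 gives J = 6 "if all planned SSS assessments are performed". Protocol Table 1 shows them as 3–4 h, 5–6 h, 8–10 h, Day 2, Day 3 and Day 7.
- Covariance terms, estimation and degrees of freedom: SAP 8.2.1.
- For the numerical illustration only (assumed): 94 subjects, six visits, complete data, simulated values.

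**Parameter count.** The marginal covariance is V = s²J + R, where s² is the intercept variance, J the all-ones matrix and R the residual covariance. For T visits an unstructured R has T(T+1)/2 parameters. For any s², replacing R by R − s²J leaves V unchanged, so s² adds nothing that can be estimated.

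| T | Where it applies | Requested | Identifiable (rank) |
|---|---|---|---|
| 5 | visits through Day 3 | 15 + 1 = 16 | 15 |
| 6 | visits through Day 7 | 21 + 1 = 22 | 21 |
| 8 | visits through Day 28 (NPRS) | 36 + 1 = 37 | 36 |

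**Flat likelihood.** In the simulated data, V was held at the sample covariance and split between s² and R in four ways:

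| s² | −2 REML log-likelihood | Day 7 estimate | SE |
|---|---|---|---|
| 0 | 669.09910423 | −0.165 | 0.337 |
| 0.489 | 669.09910423 | −0.165 | 0.337 |
| 0.979 | 669.09910423 | −0.165 | 0.337 |
| 1.762 | 669.09910423 | −0.165 | 0.337 |

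The rows are identical, as the algebra requires. The redundancy does no harm to the estimate itself; the risk lies in the fitting.

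**Information matrix.** For unstructured alone (21 × 21) the rank is 21 and the condition number about 1.2 × 10³, so it is invertible. With the random intercept added (22 × 22) the rank is still 21 and the condition number about 2.7 × 10¹⁷, which is singular to machine precision. Kenward-Roger needs this matrix inverted.

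**Fallback structures with the intercept kept.** Intercept plus compound symmetry has 3 parameters and rank 2, so it is redundant again. If the extra parameter is counted, it adds 2 to that model's AIC with no gain in fit. Intercept plus AR(1) has 3 parameters and rank 3, so it is identifiable.

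**What a wrongly imposed equal variance could do.** This is an illustration under assumed standard deviations (SDs), with complete data and residual SDs falling linearly over the six visits. Compound symmetry pools to about the mean variance, so the ratio of reported to correct SE at a visit is √(mean variance) / SD at that visit.
- Constant SD: ratio 1, no error.
- SD from 1.5 to 1.0: mean variance (2.25 + 1.96 + 1.69 + 1.44 + 1.21 + 1.00)/6 = 1.592, pooled SD 1.262. The Day 7 SE is about 26% too large. At 3 hours, 1.262/1.5 = 0.84, about 16% too small.
- SD from 2.0 to 1.0: mean variance (4.00 + 3.24 + 2.56 + 1.96 + 1.44 + 1.00)/6 = 2.367, pooled SD 1.538. The Day 7 SE is about 54% too large. At 3 hours, 1.538/2 = 0.77, about 23% too small.

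**The case against.** The over-parameterisation is not open to dispute; its consequences are. A reader might infer four stronger things that the documents do not support.

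**That the model will probably fail.** Nothing shows this. Software may set the intercept variance to zero, converge and return the unstructured fit. A Hessian warning on a fit that has converged does not literally meet the SAP's trigger either. Failure is possible, not shown to be likely.

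**That the analysis is then forced into compound symmetry or AR(1).** The SAP gives these two only as examples. The opening of 8.2 also allows covariates to be removed and other estimation routines to be tried if a model fails to converge, and 8.2.1 requires an appendix on all models tested. A switch would therefore be disclosed. What remains is that neither place says to refit unstructured without the intercept, so this is left to discretion after a failure. Nor would every failure be spurious: 8.2.2, 8.2.4 and 8.2.5 are restricted to baseline subsets, the SAP notes unexpectedly few severely neurotoxic patients, and NPRS to Day 28 needs 36 covariance parameters. Unstructured could fail there because data are sparse. The redundancy makes the two causes hard to tell apart.

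**That every secondary MMRM is affected.** Sections 8.2.7 and 8.2.13 specify an MMRM without citing 8.2.1.

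**That a confirmatory conclusion is at stake.** Section 8.2 treats these analyses as exploratory, and they lie outside the fixed testing sequence. The primary endpoint and three key secondaries use ANCOVA, and antivenom use is analysed by proportional odds.

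**Conclusion.** The point stands as a specification error of limited reach. As written, the covariance model in SAP 8.2.1 has one parameter too many (22 requested, 21 identifiable for six visits), whatever the data turn out to be. The practical consequence is conditional. If the software sets the intercept variance to zero, estimates and standard errors are those of the plain unstructured model. If the fit fails instead, a simpler structure may be adopted for a reason unrelated to the data, and visit-specific standard errors may be wrong. The sizes shown for that error depend on assumed SD patterns and complete data; the documents give no visit-specific SDs, and with constant SDs the error is nil.

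The analyses exposed are those in 8.2.1, 8.2.2, 8.2.4, 8.2.5, 8.2.6, 8.2.14 and 8.2.15, all exploratory. The primary and key secondary results do not depend on this model.

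**What to change.** Amend the covariance text in SAP 8.2.1, so that the sections referring to it follow:

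1. Fit an unstructured residual covariance with no random intercept and Kenward-Roger degrees of freedom.
2. Go to the fallback only if that model fails to converge, and say whether a Hessian that is not positive definite counts as failure.
3. In the fallback, add heterogeneous-variance structures ahead of compound symmetry. The present text names none, so this is new wording.
4. Use compound symmetry without a random intercept. A random intercept may be kept with AR(1), where it is identifiable and loosens a restrictive structure for unevenly spaced visits. A blanket deletion would go too far for that reason.

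The first step also brings 8.2.1 into line with 6.1.2 on the random intercept. The cost is a few lines of text before database lock, with no change to data collection, sample size or the testing sequence.

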- s PLA₂ sampling will be performed for all subjects on Day 1 (pre-dose and 1, 3, 6, and 9 hours post-first dose), and on Day 2, Day 3, and Day 7 (pre-dose). sPLA₂ in serum and PK samples will be processed and analyzed in a central laboratory, not at individual sites.
- PK sampling will only be performed for a total of 20 adult and pediatric subjects on Days 1 and 3, and all subjects on Day 7. Once 20 subjects have provided PK samples for Days 1 and 3, sites will be notified by the sponsor to discontinue Day 1 and 3 PK sampling. Subjects will be enrolled for PK analysis as follows: Day 1 20 subjects, pre-dose and 0.5, 1, 2, 4, 6, 8, and 12 (pre-second dose) hours; Day 3 20 subjects, pre-dose and 0.5, 1, 2, 4, 6 hours; Day 7 all subjects, pre-dose.

Figure 1 Study Schematic

- a. Because snakebite subjects are considered critically ill and will arrive in an emergency department setting, Screening, Baseline evaluation, randomization, and treatment must all take place on Study Day 1
- b. Assessments (see Schedule of Events) must be performed at the following times post-initial dose: 3 to 4 hours, 5 to 6 hours, 8 to 10 hours, 2 days (12 to 18 hours after last Day 1 measurements), 3 days (approximately 24 hours after Day 2 measurements), 7 days ± 1 day, 14 days ± 2 days, and 28 days ± 3 days
- c. The varespladib-methyl dosing for adult subjects is a 500 mg loading dose, a 250 mg dose approximately 12 hours later, then 250 mg BID for the remainder of the study period; pediatric subjects (ages 5 to < 18) will be administered doses of varespladib-methyl determined by allometric scaling, provided as 50 mg capsules, depending on age (see Section 7.3). Abbreviations: BID = twice daily; SOC = standard of care; yr = years

3		TABLE OF CONTENTS	
1	APF	PROVAL SIGNATURES	2
2	PRO	OTOCOL SUMMARY	3
	2.1	Synopsis 3	
	2.2	Schedule of Events	9
3	TAI	BLE OF CONTENTS	14
	3.1	List of In-text Tables	18
	3.2	List of In-text Figures.	18
4	LIS	Γ OF ABBREVIATIONS AND DEFINITION OF TERMS	19
5	INT	RODUCTION	20
	5.1	Background and Rationale	

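### If the unstructured MMRM in SAP 8.2.1 fails, both fallback structures it names force one residual variance on all visits, so per-visit standard errors can be wrong

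*SAP*

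**What the plan says.** SAP 8.2.1 (complete SSS through Day 7) sets up the model in three steps.

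- Mean and random part: "Analyses will include a random intercept and the fixed effects of treatment", baseline total SSS, age group, baseline neurotoxicity, visit and treatment-by-time.
- First-choice covariance: "An unstructured covariance model will be used to model the within-subject errors", with Kenward-Roger degrees of freedom.
- Fallback on non-convergence: "simpler structures (e.g., first-order compound symmetry and then autoregressive order-1 structures) will be tested" in a model without the treatment effect. The best fit, "as determined by Akaike's Information Criterion, will be used in the full model".

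The target is stated plainly: "Within this model, the estimate of interest is the effect of treatment at each time point", tested at 5% with a 95% CI at each visit. No heterogeneous-variance structure and no robust variance is named.

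The visits are far from evenly spaced. Protocol 2.2 (Figure 1, note b) lists "3 to 4 hours, 5 to 6 hours, 8 to 10 hours, 2 days", then Day 3 and Day 7.

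The models for the neurologic subscore (8.2.2), free hemoglobin (8.2.4), CK (8.2.5), NPRS (8.2.6), PGIC (8.2.14) and PSFS (8.2.15) refer back to 8.2.1. The opening of 8.2 labels all of these analyses exploratory.

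**The concern.** Compound symmetry (CS) and AR(1) each have two parameters: one variance and one correlation. Adding the planned random intercept adds the same amount to the variance at every visit, so it does not relax this. AIC cannot help either, because both named candidates share the restriction. A per-visit confidence interval then uses a variance averaged over visits, while patients are at very different stages of illness at 3 hours and on Day 7.

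The fallback can be reached for two reasons. First, a random intercept on top of an unstructured residual matrix is not identifiable. The marginal covariance is R + σ_b²J (J a matrix of ones), and R can absorb σ_b²J. For six visits that is 21 + 1 = 22 parameters for a matrix with 6×7/2 = 21 distinct elements. Second, several models run in baseline-abnormal subsets (neurologic subscore ≥ 1 and ≥ 2, free hemoglobin ≥ 15 mg/dL, CK ≥ 2 times reference). SAP 8.2.2 says neurologic outcomes were not made primary or key secondary "because of the unexpectedly small number of severely neurotoxic patients enrolled in the trial".

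At stake are the per-visit p-values and intervals in the supportive efficacy tables.

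**Working it through.** **Inputs.** The documents give no SD by visit. The only SSS SD is 1.75, for the five-subscore primary change (SAP 3.2). With it, the plan's figure reproduces: 47 per arm and a difference of 1.1 give 85.4% power by noncentral t, against the stated 85%. That says nothing about how variance changes over time, so the SDs below are assumptions. Visit times are 3.5, 5.5, 9, 24, 48 and 168 h, from the protocol windows.

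**Formula.** With complete data and a mean for each arm and visit, the estimate at a visit is the difference in visit means whatever the covariance structure. Its standard error depends only on the fitted variance at that visit. Under CS the fitted variance is the average of the visit variances, so

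ratio at visit j = model SE / true SE = √(mean of SD²) / SD_j; size = 2[1 − Φ(1.96 × ratio)].

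**Without baseline adjustment.** For SDs of 2.5, 2.4, 2.2, 1.8, 1.4, 1.0 the variances sum to 23.05. The mean is 3.842 and its root 1.960. At 3–4 h the ratio is 1.960/2.5 = 0.78; at Day 7 it is 1.960/1.0 = 1.96.

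| Assumed SD, 3–4 h to Day 7 | | 3–4 h | 5–6 h | 8–10 h | Day 2 | Day 3 | Day 7 |
|---|---|---|---|---|---|---|---|
| 2.5, 2.4, 2.2, 1.8, 1.4, 1.0 | ratio | 0.78 | 0.82 | 0.89 | 1.09 | 1.40 | 1.96 |
| | size % | 12.4 | 10.9 | 8.1 | 3.3 | 0.6 | <0.1 |
| 2.2, 2.15, 2.05, 1.9, 1.7, 1.5 | ratio | 0.88 | 0.90 | 0.94 | 1.02 | 1.14 | 1.29 |
| | size % | 8.5 | 7.8 | 6.5 | 4.6 | 2.6 | 1.2 |
| 1.75 throughout | size % | 5.0 | 5.0 | 5.0 | 5.0 | 5.0 | 5.0 |
| 1.4, 1.5, 1.6, 1.8, 2.0, 2.2 | size % | 1.3 | 2.1 | 3.0 | 5.4 | 8.2 | 11.4 |

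AR(1) gives nearly the same values (up to 13.1% in the first case). Sizes for the two falling patterns span about 0 to 13%.

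**With baseline adjustment.** The SAP model includes baseline SSS. With a visit-specific baseline slope (SAP 6.1.2 lists baseline-by-time), the residual variance is SD_j²(1 − ρ_j²), where ρ_j is the correlation with baseline. I took ρ = s + (1 − s)exp(−hours/τ), with s from 0 to 0.3 and τ from 12 to 96 h.

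- SD 2.5 to 1.0: CS sizes run from 0.1% to 10.8%, and the worst visit is 8–10 h, Day 2 or Day 3.
- SD 2.2 to 1.5: sizes run from near 0% to 17.3%. Worst case, s = 0.3 and τ = 96: residual variances are 0.240, 0.353, 0.510, 1.031, 1.373 and 1.850, with mean 0.893. The Day 7 ratio is √(0.893/1.850) = 0.69, size 17.3%. The 3–4 h ratio is √(0.893/0.240) = 1.93, size near 0%. This is the reverse of the unadjusted pattern. Taking s to 0.5 raises the maximum to 18.5%.

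**Is AR(1)'s equal spacing the cause?** With SD flat at 1.75 and correlation decaying in real time (0.8 per 24 h), AR(1) has the spacing wrong but its ratio is 1.00 at every visit. The common variance is the cause.

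**Alternatives.** Heterogeneous compound symmetry (CSH) has ratio 1.00 at every visit if correlation is exchangeable. Under real-time decay (s 0 to 0.5, same τ) its sizes were about 1 to 7% unadjusted and 3 to 6% adjusted. Heterogeneous Toeplitz, which ties correlation to visit lag, gave about 9 to 14% at 3–4 h and at most 2.3% at Day 3 and Day 7, unadjusted.

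**AIC.** With SD 2.0 to 0.8 and correlation 0.8 per 24 h, AIC is 482 for AR(1), 678 for CSH and 735 for CS (lower is preferred). Yet AR(1)'s ratios run from 0.80 to 2.00 and CSH's from 0.94 to 1.32. AIC rewards the fit of the correlations, not the per-visit variances.

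**The case against.** The plan's defence has real weight. The structures apply only after non-convergence and are introduced as examples. SAP 8.2 also allows other estimation routines, and every tested model is to be reported in a CSR appendix, so CSH could be tried without an amendment. At 94 patients, a six-visit unstructured fit may well converge once the random intercept is gone; a simulation at that size gave 4.4 to 5.3% at every visit. The analyses are exploratory. All of this stands and limits the weight of the point. But an open list means the choice is made after the data are seen, which is the reason to name it now.

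Several stronger readings are tempting and are not supported:

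- *Intervals too narrow on Day 1 and far too wide by Day 7.* That needs a falling residual SD. It is plausible as scores approach zero, but no SD by visit is given, and baseline adjustment can reverse it. So can deaths. Protocol 10.3.1.1 scores death at the maximum in each section, 5×3 + 2×4 = 23 for the complete SSS. One death among 47, with survivors at mean 1 and SD 0.8, gives a mean of 69/47 = 1.468. The SD is then √[(46×0.64 + 46×0.468² + 21.532²)/47] = 3.27.
- *Unequal spacing distorts the per-visit errors.* Not in complete data, as shown.
- *Every MMRM is affected.* Kidney markers (8.2.7) and CGI-I (8.2.13) do not refer to 8.2.1, and the neurologic, free hemoglobin and CK models stop at Day 3.

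**Conclusion.** The point holds in conditional form. The only fallbacks named impose a common variance on an analysis whose stated result is visit-specific. If residual variance differs by visit, per-visit tests and intervals are miscalibrated. For an SSS SD falling from 2.5 to 1.0 or from 2.2 to 1.5, size is about 0 to 13% unadjusted and about 0 to 17% adjusted for baseline, against a nominal 5%. With flat variance there is no error. Which visits are affected cannot be told from the documents.

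These figures rest on assumed SDs and correlations, large-sample theory, complete data and the same covariance in both arms. They do not describe the small subsets, where the fallback is most likely.

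A reader might infer that the trial's main conclusion is exposed. It is not: the primary and key secondary endpoints use ANCOVA or proportional-odds regression. This is a cheap improvement to the exploratory MMRMs for complete SSS, neurologic subscore, free hemoglobin, CK, NPRS, PGIC and PSFS.

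**What to change.** Amend SAP 8.2.1, while still blinded, as follows:

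1. Remove the random intercept; the unstructured matrix already covers it.
2. If the unstructured fit still fails, use heterogeneous compound symmetry with Kenward-Roger.
3. If that fails, use compound symmetry with an empirical (sandwich) variance and a small-sample correction.
4. Apply this as a fixed order, not by AIC.
5. Drop AR(1), and do not put heterogeneous Toeplitz first, since it also works by visit lag.

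The sections that refer to 8.2.1 inherit the change. It would help to state in the same place whether deaths enter the MMRM at the maximum score, since that can dominate the late-visit variance.

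The cost is a few sentences. Heterogeneous compound symmetry needs 6 variances + 1 correlation = 7 covariance parameters for six visits instead of 2, well below the 21 of the unstructured matrix. It is not exact when correlation decays with time, but in the cases checked it was much closer to 5% than either named fallback.
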